	All subjects who received at least one Therapeutic Dose of Ultratrace iobenguane I 131 will be included in the Full Analysis Set; all subjects who received both Therapeutic Doses and who attended the 3 Month and 6 Month Efficacy Visits with no major Protocol violations will be included in the Per Protocol Set. For each of these populations, a point estimate (with a 95% confidence interval, using the normal approximation with a continuity correction) for the proportion of subjects experiencing a reduction in use of all antihypertensive medication by at least 50% for at least six months or two cycles will be calculated. This single arm trial will be considered a

success if the lower limit of the two-sided 95% confidence interval for the Full Analysis Set exceeds 0.10 (10%).

Secondary analyses of the primary efficacy endpoint and analyses of the secondary efficacy endpoints will be conducted as described in the protocol and Statistical Analysis Plan.

Safety analyses will include treatment emergent adverse events, clinical laboratory measurements, vital signs measurements, and physical examination findings. Adverse events and incidence of overall toxicity, categorized by toxicity grades (severity), will be described. All subjects who received the Imaging Dose of Ultratrace iobenguane I 131 will be included in the analysis of any safety endpoint. Adverse events will be captured for all enrolled subjects and those prior to the Imaging Dose will be displayed in a separate listing.

Sponsor Contact Information

Main Telephone Number for Business Hours 8:30 AM – 5:00 PM EST	
Worldwide Safety Hotline	
MD Executive Vice President, Research & Development Medical Monitor	
Clinical Trial Manager	

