Use of antihypertensive medication will be measured through standard, ongoing reporting of concomitant medications throughout the study until completion of the follow-up period. Tumors will be measured by computed tomography (CT) with contrast or magnetic resonance (MR) imaging at baseline and at 3, 6, 9 and 12 months after the first Therapeutic Dose. Obtaining renal volume for each kidney is required at baseline. A bone scan will be performed at Screening/baseline and if probable metastatic disease is observed or suspected, additional bone scans will be performed at Month 3, 6, 9, 12. Overall tumor response at 3, 6, 9 and 12 months per RECIST criteria will be assessed centrally by independent, blinded readers. FDG scans may also be performed at baseline and 3, 6, 9, and 12 months to assess viable tumor tissue. Tumor markers [serum chromogranin A, plasma free metanephrines and normetanephrines, 24 hour urinary vanillylmandelic acid (VMA), plasma catecholamines (dopamine, epinephrine and norepinephrine), 24 hour urinary catecholamines (dopamine, epinephrine and norepinephrine) and urinary metanephrines and normetanephrines] will be evaluated by a central laboratory. Testing for tumor markers will occur at baseline, every two weeks for the first 24 weeks after the first Therapeutic Dose starting at Week 2, and monthly during months 7-12. Renal function will be assessed through either creatinine clearance or Glomerular Filtration Rate (GFR) at baseline and at the Months 6 and 12 Efficacy Visits. Evaluation of thyroid function (T3, T4 and TSH) and clinical evaluation of possible dry mouth will be performed at the 12 month Efficacy Visit. Use and dose of antihypertensive, pain and other medication required for tumor associated signs and symptoms will be recorded on an on-going basis throughout the study until completion of the follow-up period. Subject-reported Quality of Life measurements will be obtained through the EORTC QLQ-C30 v3 and the NIH Quality of Life and Symptoms Questionnaire for Pheochromocytoma and Paraganglioma. The frequency of the procedures is summarized in the Schedule of Procedures (Appendix VII). Subject may undergo additional assessments as warranted (for example, to confirm tumor response) at unscheduled visits.

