10.5 Blinding and Randomization

This is an open-label, single arm study.

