11.7 CT or MR Image Evaluation

Off-site CT and MR assessment will be conducted by independent, CT and MR-experienced readers in accordance with the charter issued by the imaging core laboratory. These readers will be blinded to clinical subject information as described in the Imaging Charter. The readers will determine objective tumor response according to RECIST criteria. On-site interpretation of CT and MR images may also be done, but only the results of the blinded read will be used for the objective tumor response evaluations.

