7.4.7. Tumor Markers

Tumor markers (e.g., serum chromogranin A) will be assessed as stated in the Schedule of Procedures. For each individual tumor marker, results will be categorized per the response criteria in the following table. If the tumor marker value prior to dosing is less than 1.5 times the upper limit of normal for the respective marker, it will not be included in this analysis.

Response	Criteria for Response
Complete Response (CR)*	Normalized, at or below upper limit of normal (ULN)
Partial Response (PR)*	$\geq 50\%$ decrease in baseline value but above the ULN
Stable Disease (SD)	Any response other than CR, PR or PD
Progressive Disease (PD)	$\geq 50\%$ increase in baseline value
Not Evaluable (NE)	Below 1.5 X ULN at baseline, or baseline missing

* To be assigned a status of CR or PR changes in tumor marker measurements must be confirmed by repeat assessments

For the Full Analysis Set, summary tables for confirmed tumor marker response, for each marker, will be prepared by visit window and all measurements of tumor markers will be listed. A confirmed response will require that the subsequent tumor marker assessment be identical or better compared with the previous response assessment.

Subjects will be evaluated to determine the best confirmed response for each tumor marker that is ≥ 1.5 x ULN at baseline. A listing of the best confirmed response for each tumor marker, at what time it becomes apparent, and the duration of any positive response (CR or PR) will be generated. The response is considered to be ended when the tumor marker response becomes confirmed at SD or PD.

Each subject will also be evaluated to determine if that subject is an overall tumor marker responder. An overall responder will be a subject who achieves a best confirmed response of either CR or PR at some time point, on each of the plasma and urine tumor markers that were abnormal at baseline, with the exception of urine VMA.

An additional analysis will be performed where the tumor marker response will be summarized for the dominant tumor marker for each subject. The dominant tumor marker will be identified prior to database lock by the Medical Monitor.

Analysis will determine if there is an association between achieving an overall best tumor marker response of CR or PR with achieving primary endpoint responder status based on the reduction in antihypertensive medications.

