11. LIST OF PLANNED TABLES, LISTINGS AND FIGURES

The tables, listings and figures listed below will be prepared in accordance with the descriptions provided in this SAP.

Tables:

Table 14.1.1	Disposition (Population: Enrolled)
Table 14.1.2	Subject Characteristics (Population: Safety)
Table 14.1.3	Medical History (Population: Safety)
Table 14.1.4	Cancer History (Population: Safety)
Table 14.15	Prior Treatment for Cancer (Population: Safety)
Table 14.2.1.1A	Primary Endpoint: Decrease in Use of Antihypertensive Medications (Population: Full Analysis Set)
Table 14.2.1.1B	Primary Endpoint: Decrease in Use of Antihypertensive Medications (Population: Per Protocol Set)
Table 14.2.1.1C	Primary Endpoint: Decrease in Use of Antihypertensive Medications: Sensitivity Analysis (Population: Full Analysis Set)
Table 14.2.1.1D	Primary Endpoint: Decrease in Use of Antihypertensive Medications: Sensitivity Analysis (Population: Full Analysis Set)
Table 14.2.1.2A	Duration of Clinical Benefit (Population: Full Analysis Set)
Table 14.2.1.2B	Duration of Clinical Benefit (Population: Per Protocol Set)
Table 14.2.2.1	Tumor Response Assessment per RECIST Criteria (Population: Full Analysis Set)
Table 14.2.2.2	Tumor Response Assessment per RECIST Criteria Modified to Include Moderate Response (Population: Full Analysis Set)
Table 14.2.2.3	Tumor Response Assessment per RECIST Criteria by Primary Endpoint Status (Population: Full Analysis Set)
Table 14.2.2.4	Tumor Response Assessment per RECIST Criteria Modified to Include Moderate Response by Primary Endpoint Status (Population: Full Analysis Set)
Table 14.2.2.3	Bone Lesions (Population: Full Analysis Set)
Table 14.2.2.4	Bone Lesions: Shift from Baseline by Visit
Table 14.2.3.1	Tumor Marker Response Proportions (Population: Full Analysis Set)
Table 14.2.3.2	Tumor Marker Response Proportions by Dominant Tumor Marker (Population: Full Analysis Set)
Table 14.2.3.3	Spearman Correlation between Tumor Marker Response Proportions and relative change in tumor marker by Tumor Marker (Population: Full Analysis Set)
Table 14.2.3.4	Spearman Correlation between Tumor Marker Response Proportions & Overall Tumor Response (Population: Full Analysis Set)
Table 14.2.35	Spearman Correlation between Response Proportions & Best Overall Tumor Response (Population: Full Analysis Set)
Table 14.2.3.6	Tabulation of Best Overall Confirmed Tumor Marker Response with Best Overall Tumor Response

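### SAP 7.4.7 neither defines the dominant tumor marker nor restricts its choice to pre-dose data, so selection that depends on response is not prevented

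*SAP*

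**What the plan says.** SAP 7.4.7 first categorises response for each marker separately, then defines an overall responder, and then adds a third summary: "An additional analysis will be performed where the tumor marker response will be summarized for the dominant tumor marker for each subject". The next sentence is the whole of the selection procedure: "The dominant tumor marker will be identified prior to database lock by the Medical Monitor". The output is Table 14.2.3.2, listed in SAP section 11 as "Tumor Marker Response Proportions by Dominant Tumor Marker (Population: Full Analysis Set)".

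The only limit on the candidates is the evaluability threshold in the same section: "Subjects will be evaluated to determine the best confirmed response for each tumor marker that is ≥ 1.5 x ULN at baseline". The protocol's marker sections (11.5.10 and 13.3.2.2.2) do not mention a dominant marker.

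On design, Protocol 10.5 states: "This is an open-label, single arm study". On data flow, Protocol 9.1 states: "Testing for tumor markers will occur at baseline, every two weeks for the first 24 weeks after the first Therapeutic Dose", with monthly testing in Months 7 to 12. SAP 4.1 records that enrollment had finished in December 2015, so post-dose marker data were already accruing or in hand when that text was written.

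**The concern.** A deadline at database lock fixes when the choice must be finished. It does not fix what may be looked at while choosing. All scheduled marker results through Month 12 can exist before lock, and nothing in either document separates the person who chooses from those results. The Medical Monitor appears in the sponsor contact list of the protocol's study outline. Where the plan wants an assessment kept apart from clinical information it says so, as for the CT and MR readers in Protocol 11.7: "These readers will be blinded to clinical subject information as described in the Imaging Charter". Marker selection has no counterpart.

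The other steps of the marker analysis follow stated criteria: the response cut-offs, confirmation by the subsequent assessment, and the overall-responder definition. This step is left to judgement. If a subject has several qualifying markers and one responded, an unrestricted choice can settle on that one. At stake is whether the proportion in Table 14.2.3.2 can be read as a response rate on a marker chosen independently of response. With no control arm, any such selection would not cancel in a comparison.

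**Working it through.** **The plan's own figure.** There is none to reproduce. The documents give no expected rate, sample size, alpha or success criterion for the dominant-marker summary. The sample size of 58 belongs to the primary endpoint and is not touched.

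**Room for choice.** Protocol 9.1 lists:
- serum chromogranin A (1)
- plasma free metanephrines and normetanephrines (2)
- urinary VMA (1)
- three plasma catecholamines (3)
- three urinary catecholamines (3)
- urinary metanephrines and normetanephrines (2)

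That is 1 + 2 + 1 + 3 + 3 + 2 = 12 analytes. Scheduled post-dose assessments are 12 (Weeks 2 to 24, every two weeks) plus 6 (Months 7 to 12), or 18 per subject. The threshold of 1.5 x ULN at baseline reduces the candidates but does not choose among those that pass.

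**Assumed inputs.** The documents give neither the number of qualifying markers per subject (k) nor the correlation between marker responses (rho). I take k = 2, 3 and 5, and rho from 0.3 to 0.9. For the per-marker response rate p, I use 30% as a plain assumption. I also use 45%, the biochemical response proportion that Protocol 7.2 reports from a literature review of the carrier-added product. All markers are given the same p.

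**Formula.** If the marker is always one that responded whenever any did, the reported rate is the probability that at least one of k responds. With independent markers this is 1 - (1 - p)^k. For example, p = 0.30 and k = 2 give 1 - 0.70^2 = 0.51. With correlated markers I use an equicorrelated normal model. Given a common factor u, each marker responds with probability c(u) = Phi[(z_p - sqrt(rho) u) / sqrt(1 - rho)], where z_p is the standard normal quantile of p. The rate is then 1 - E[(1 - c(u))^k], with the expectation over a standard normal u, integrated numerically.

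**Results: probability that at least one of k responds.**

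| p | rho | k = 2 | k = 3 | k = 5 |
|---|---|---|---|---|
| 30% | 0.3 | 47% | 58% | 71% |
| 30% | 0.5 | 44% | 53% | 63% |
| 30% | 0.7 | 41% | 47% | 55% |
| 30% | 0.9 | 36% | 40% | 44% |
| 45% | 0.3 | 65% | 76% | 86% |
| 45% | 0.5 | 62% | 70% | 79% |
| 45% | 0.9 | 52% | 56% | 60% |

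For k = 1 there is no choice, and the rate stays at p. Under the equal-rate assumption it also stays at p for any k if the marker is fixed without reference to response. The gap between each cell and p is the largest inflation the model allows. It is not a forecast.

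**The case against.** The strongest objection concerns what is known. A reader might infer that the Medical Monitor chooses with post-dose results in view, and hence that Table 14.2.3.2 is biased. The documents do not support that. They say that a central laboratory evaluates the markers and that the study is open-label. They do not say what data are used to name the dominant marker, and the word could mean the secretory pattern at baseline. This stands: access is inferred, and outcome-driven choice is possible but not shown.

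A reader might also infer that an endpoint of the trial is compromised. That does not hold either. The analysis is additional and descriptive, is absent from the protocol's endpoint list and carries no alpha. The secondary endpoint of tumor marker response is reported through per-marker tables, and all measurements are listed, so a reader could set the chosen marker beside the others. The overall-responder definition requires CR or PR on every plasma and urine marker abnormal at baseline except urine VMA, which is the opposite of taking the best one.

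The size is also open to challenge. Protocol 7.4 says that chromogranin A correlates well with plasma metanephrines, so high values of rho are plausible, and the inflation is smallest there. Some subjects may have only one qualifying marker. Both points are fair, and they are why the range runs to rho = 0.9 and is called an upper bound.

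The objection does not supply a definition, a pre-dose restriction or a separation of the selector from results. None of these is in either document.

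**Conclusion.** The point holds as a gap in the procedure: the plan permits selection that depends on response, and such selection can inflate the proportion in Table 14.2.3.2. It does not show that this happened or would happen.

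Under fully outcome-driven choice, the upper bound over rho 0.3 to 0.9 runs from 6 points (36% against 30%, two markers, rho 0.9) to 41 points (71% against 30%, five markers, rho 0.3). With two or three markers at a 45% rate the bound is 52-65% and 56-76%. The rates, the number of qualifying markers, the correlation and the equal-rate assumption are mine.

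The matter is worth correcting before lock because the table is planned output and the correction is cheap. It has no bearing on the trial's success criterion.

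**What to change.** Amend the sentence in SAP 7.4.7 so that the dominant marker is identified from pre-dose values only, among markers at or above 1.5 x ULN at baseline. Either route is enough:

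- **Programmed rule.** For example, take the largest baseline multiple of ULN, with a fixed order for ties. Two cautions apply. Protocol 7.4 describes catecholamine secretion as episodic, so this rule favours markers caught at a high point, and regression to the mean could itself raise the rate of 50% decreases. The SAP 7.4.7 rule that sets values outside the reportable range to a limit of normal should not be applied to the ranking, because a very high baseline would then rank at 1 x ULN and fall below the threshold.
- **Documented judgement.** The Medical Monitor chooses from a dated, filed listing that shows baseline values only.

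The restriction to pre-dose values is the firm part; the particular ranking rule is open to debate. The cost is one SAP sentence and one derivation or listing, and possibly a less favourable proportion. Trial conduct, sample size and the primary analysis do not change.

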Additional correlations between tumor marker responses and other endpoints may be performed as exploratory analyses.

Correlations using the tumor marker response for each tumor marker will be performed at the 3, 6, 9, and 12 month visit windows. These correlations are listed below.

- Tumor marker responses among the different tumor markers.
- Tumor marker response and overall unmodified RECIST response will also be performed: tumor response will be coded as 1 (CR), 2 (PR), 3 (SD), and 4 (PD).
- An additional analysis, tabulating the best overall confirmed tumor marker response and best overall RECIST response through 12 months post first therapeutic dose, will also be performed. For this analysis, the best overall confirmed tumor marker response and the best overall RECIST tumor response will be treated as binary variables, with responses of CR and PR combined as a positive response and SD and PD combined as a negative response.

Spearman correlation coefficients will be reported for all correlations, and Fisher's exact test will be used for binary response comparisons.

For the purposes of tabulations, tumor marker evaluations where there is a comment that the value is above or below the clinical reportable range will be set to the upper or lower limit of normal as applicable.

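### SAP 7.4.7 recodes off-scale-high tumor markers to the upper limit of normal, so a rising marker can tabulate as a confirmed CR and an off-scale-high baseline becomes Not Evaluable

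*SAP*

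**What the plan says.** All the operative text is in SAP Section 7.4.7.

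- **Off-scale results.** The rule opens "For the purposes of tabulations, tumor marker evaluations where there is a comment" and goes on that the "value is above or below the clinical reportable range will be set to the upper or lower limit of normal as applicable". It makes no exception for baseline values and has no separate rule for the high side.
- **Categories.** CR is a value at or below the ULN. PR is a fall of at least 50% from baseline that stays above the ULN. PD is a rise of at least 50%. SD is the remainder.
- **Entry.** Not Evaluable (NE) is "Below 1.5 X ULN at baseline, or baseline missing". The text repeats that a pre-dose value "less than 1.5 times the upper limit of normal for the respective marker, it will not be included in this analysis".
- **Confirmation.** "To be assigned a status of CR or PR changes in tumor marker measurements must be confirmed by repeat assessments", and "A confirmed response will require that the subsequent tumor marker assessment be identical or better compared with the previous response assessment". No minimum interval is given.
- **Overall responder.** CR or PR is needed "on each of the plasma and urine tumor markers that were abnormal at baseline", urine VMA excepted.

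Protocol Section 13.3.2.2.2 defines the same CR and requires the repeat at least four weeks later. It has no rule for off-scale results, so nothing there corrects the SAP sentence.

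**The concern.** A result above the reportable range is among the highest the laboratory can see. The SAP gives it the largest value that still counts as normal. The wording may be a slip for the limit of the reportable range, but it is the only instruction on off-scale results, and a programmer following it would score progression as response.

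The outputs exposed are the response proportions (Table 14.2.3.1), the dominant-marker table (14.2.3.2) and the tabulation against best RECIST response (14.2.3.6). Section 7.4.7 also plans an association between marker response and primary-endpoint responder status. There is no control arm in which the artefact would show.

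**Working it through.** **Inputs.** All values are in units of ULN. The categories, the 1.5 entry rule and the confirmation rule come from SAP 7.4.7. The upper reportable limit U is not in the documents; U = 10 is assumed for the examples.

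**Coding.** With baseline b and follow-up v:
- NE if b < 1.5
- otherwise CR if v ≤ 1
- otherwise PR if v ≤ 0.5b
- PD if v ≥ 1.5b
- SD if none of these

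A CR is confirmed if the next value is CR. A PR is confirmed if the next value is PR or CR. The SAP rule replaces any value above U by 1.0.

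**Worked cases (U = 10).**

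| Baseline | Follow-ups | True reading | After SAP recoding | SAP result |
|---|---|---|---|---|
| 5 | 15, 15 | 15/5 = 3.0: PD, PD | 1.0, 1.0 | Confirmed CR |
| 5 | 15, 0.9 | PD, then unconfirmed CR | 1.0, 0.9 | Confirmed CR |
| 5 | 2.4, 15 | 2.4/5 = 0.48: PR, not confirmed | 2.4, 1.0 | Confirmed PR |
| 12 | 0.8, 0.8 | Confirmed CR | baseline 1.0 < 1.5 | NE |
| 5 | 15, 6 | PD, then 6/5 = 1.2: SD | 1.0, 6 | CR criterion met once, not confirmed |

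The last row matters: one isolated off-scale value does not by itself create a confirmed response.

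**Dependence on the assumed limit.** With U = 5, 10, 20 and 50 and baselines of 1.5, 3, 0.5U, 0.7U and 0.9U, two off-scale-high follow-ups read CR, CR in every case under the SAP rule. An off-scale-high baseline was NE in every case, including after a true fall to 0.4U or to 0.9. The result is a property of the rule and does not depend on U.

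**The same cases with the value set to U.** Two off-scale-high follow-ups read PD for baselines of 1.5, 3 and 0.5U, and SD for 0.7U and 0.9U. None reads CR. An off-scale-high baseline becomes evaluable: a later off-scale-high value is SD, a fall to 0.4U is PR and a fall to 0.9 is CR.

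**Size.** Each false confirmed response adds 1/n. Counts and denominators are assumptions. The figure 58 is the planned sample size in SAP Section 6, used only for scale, and 30 stands for a smaller evaluable set.

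| False responses | n = 58 | n = 30 |
|---|---|---|
| 0 | 0 | 0 |
| 1 | 1.7 points | 3.3 points |
| 3 | 5.2 points | 10.0 points |
| 5 | 8.6 points | 16.7 points |

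Baseline exclusions can move the proportion either way. Assume 17 true responders among 58 (29.3%) and three subjects dropped as NE. If all three are non-responders, the result is 17/55 = 30.9%. If all three are responders, it is 14/55 = 25.5%.

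**The case against.** The strongest counter-arguments are these.

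- **It is probably a slip, and raw values are listed.** Both may be so. The listings let a reader find the error, but the tables would still carry it.
- **The protocol's four-week repeat would block it.** Protocol Section 11.5.10 samples every two weeks in weeks 2–24, so two adjacent samples would not meet the protocol interval. This stands as a limit: two consecutive results suffice only under the SAP's own confirmation rule. But the SAP governs the tables, and a marker that stays off-scale for four weeks would be confirmed under either rule.
- **Progressing subjects leave.** Protocol Sections 9.7 and 9.8 discontinue subjects with progressive disease and stop their marker tests. That lowers the frequency. It does not remove the problem, because a marker rise is not stated to be study progression.
- **The rule covers only tabulations.** This stands for two possible further effects. Off-scale-high markers would drop out of the overall-responder requirement only if the recoded value also defines abnormal at baseline. An off-scale relapse would fail to end a response only if recoded values feed the duration listing. NE is different, because it is a category of the tabulated response table itself.
- **58 is not the marker denominator.** Correct. The protocol ties 58 to the Per Protocol Set, whereas marker tables use the Full Analysis Set restricted to evaluable baselines. The shifts above illustrate scale and are not estimates.

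**Conclusion.** The rule is wrong as written and should be fixed. For a marker with an in-range baseline of at least 1.5 × ULN, it turns two consecutive off-scale-high results, or one next to a truly normal value, into a confirmed CR. It also lets an off-scale-high value confirm a preceding PR. It removes markers whose baseline was off-scale high.

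Confidence is high on the logic, which follows from the text alone for any reportable limit. The effect on results cannot be computed and may be zero. It is confined to a secondary endpoint and its associations; the primary endpoint (SAP 7.4.1 and 7.4.2) does not use marker values.

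**What to change.** Replace the off-scale sentence in SAP 7.4.7 with:

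*A result beyond the reportable range of its assay takes the value of the limit it exceeded and is flagged as censored. An off-scale-high result is never scored CR. An off-scale-high baseline is evaluable if the reportable limit is at least 1.5 × ULN.*

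Report the number of flagged results per marker. Where capping leaves the category open (SD or PD, SD or PR), show the response proportions both ways.

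**Cost.** One sentence, one flag, a count per marker and, only where flagged results leave a category open, a second set of proportions. No new subject data are needed. Each assay's numeric limit is needed; the documents do not give it, so the central laboratory would have to supply it if it is not already in the data.

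**Downside.** Capping understates change (examples with U = 10):
- True PD from an in-range baseline above 0.67U shows as SD: 8 to 15 is capped to 10/8 = 1.25.
- True PD from an off-scale baseline shows as SD: 12 to 30 becomes 10 to 10.
- True PR from an off-scale baseline shows as SD if follow-up exceeds 0.5U: 40 to 6 becomes 6/10 = 0.6.
- An apparent response can end early: 40 then 4, 4, 6, 6 is PR throughout, but capped it reads PR, PR, SD, SD. Under the current rule this subject is NE.

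A marker whose limit is below 1.5 × ULN stays NE at an off-scale baseline. In a grid check with limits from 2.25 to 50 × ULN, capping created no false confirmed CR or PR; its only error at the confirmed level was a lost PR with an off-scale baseline. At the low end no category changes, provided the lower reportable limit is at or below the ULN.
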